**Table 41 Standard Definitions for Neonatal Events of interest not defined as events in GAIA**

Event of Interest	Definition
Large for gestational age	Birth weight > 90% for newborns of same gestational age in same population (>4000g at term).
Macrosomia	BW >4000 g (8 lb, 13 oz).

CONFIDENTIAL

207636 (EPI-RSV-008 BOD)  
Protocol Amendment 4 Final

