  - Functional defects
- Neonatal death,
  - Neonatal death in a preterm live birth (gestational age $\geq$ 28 to < 37 weeks)
  - Neonatal death in a term live birth
- Neonatal infections,
  - Blood stream infections
  - Meningitis
  - Respiratory infection
- Respiratory distress in the neonate,
- Preterm birth,
- Failure to thrive,
- Large for gestational age,
- Macrosomia,
- Any other neonatal event considered by the investigator to be of concern (specify, e.g. neurodevelopment delay)

For events of interest that include subcategories, the frequency of the main event of interest and of each event subcategory will be included in the analysis. The overall frequency will include infants who present at least one of the subcategory events.

**CONFIDENTIAL**207636 (EPI-RSV-008 BOD)  
Protocol Amendment 4 Final**11.1.2. Secondary endpoints**

- Pregnancy related events of interest from Visit 1 through Visit 6 (as defined in primary endpoints) for each GAIA level of diagnostic certainty (where applicable and feasible).
- Neonatal events of interest from birth through 28 days of age (as defined in primary endpoints) for each GAIA level of diagnostic certainty (where applicable and feasible).

Of note, some events of interest fall under a single category but have multiple subcategories. For each event, the investigator should identify the event and select the applicable sub-category and the GAIA level of diagnostic certainty.

- RSV-A neutralizing antibody titers in maternal blood at delivery
- RSV-A neutralizing antibody titers in cord blood at delivery.
- Episode(s) of RSV-LRTI from birth up to 1 year of age.
- Episode(s) of RSV hospitalization from birth up to 1 year of age.

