## 11.2. Determination of sample size

The target will be to enroll up to approximately 200 to 300 eligible subjects (pregnant women) by country. Subjects may drop-out from the study due to a variety of reasons, e.g. migration from the study area. Assuming a drop-out rate of about 10% during the course of follow-up, there will be up to approximately 180 to 270 evaluable subjects by country.

Considering a sample size of up to approximately 180 to 270 evaluable subjects by country, [Table 17](#) illustrates the precision (exact 95% confidence interval [CI]) one can get on the percentage of subjects with maternal, fetal and neonatal events of interest. Precision (exact 95% CI) has also been computed for a sample size of 270, 180 and 100 evaluable subjects for estimate by study site.

The percentages of subjects with maternal, fetal and neonatal events of interest for the primary objectives are expected to range from 0 to 35%.

**Table 17 Precision (exact 95% confidence interval) on the percentage of subjects with maternal, fetal and neonatal events of interest for sample size of 270, 180 and 100 subjects**

% 35 30 25 20 15 10 5 3 1 0	270 subjects			180 subjects			100 subjects		
	N 94.5 81 67.5 54 40.5 27 13.5 8.1 2.7 0	Lower 29.3 24.6 19.9 15.4 11 6.7 2.7 1.3 0.2 0.2 0	Upper 41 35.8 30.6 25.3 19.8 14.2 8.3 5.8 3.1 1.4	N 63 54 45 36 27 18 9 5.4 1.8 0	Lower 28.1 23.4 18.9 14.4 10.1 15.3 2.3 1 0.1 0	Upper 42.4 37.3 32 26.6 21.1 15.3 9.3 6.8 3.9 2	N 35 30 25 20 15 10 5 3 1 0	Lower 25.7 21.2 16.9 12.7 8.6 4.9 1.6 0.6 0 0	Upper 45.2 40 34.7 29.2 23.5 17.6 11.3 8.5 5.4 3.6
		limit limit limit limit limit limit limit limit limit limit limit	limit limit limit limit limit limit limit limit limit limit limit		limit limit limit limit limit limit limit limit limit limit limit				
35	94.5	29.3	41	63	28.1	42.4	35	25.7	45.2
30	81	24.6	35.8	54	23.4	37.3	30	21.2	40
25	67.5	19.9	30.6	45	18.9	32	25	16.9	34.7
20	54	15.4	25.3	36	14.4	26.6	20	12.7	29.2
15	40.5	11	19.8	27	10.1	21.1	15	8.6	23.5
10	27	6.7	14.2	18	6	15.3	10	4.9	17.6
5	13.5	2.7	8.3	9	2.3	9.3	5	1.6	11.3
3	8.1	1.3	5.8	5.4	1	6.8	3	0.6	8.5
1	2.7	0.2	3.1	1.8	0.1	3.9	1	0	5.4
0	0	0	1.4	0	0	2	0	0	3.6

%= Percentage of subjects with maternal, fetal and neonatal events of interest

N= Number of subjects with maternal, fetal and neonatal events of interest

Lower and upper limits are exact 95% confidence intervals

**CONFIDENTIAL**207636 (EPI-RSV-008 BOD)  

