**In all neonates live-born to women enrolled in the study:**

- To determine the frequencies of neonatal events of interest. as specified in Section [11.1.1.3](#).  
The number and percentage (with exact 95% CI) of neonates presenting the events of interest specified in Section [11.1.1.3](#) will be tabulated for each event. Missing data may be considered a separate category.

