Weight below 10th percentile for gestational age as assessed against a validated global, regional or local standard.

Levels of Diagnostic Certainty (1 highest level to 4 lowest level of certainty)	
Level	Description
1	
 
• Weight below 10th percentile for gestational age AND
 
• The following used in assessment of weight: 
 
○ Newborn weighed within 24 hours of birth
 
○ Weight assessed using a calibrated electronic scale with 10 g resolution
 
 AND
 
• The following for assessment of gestational age: 
 
○ Certain LMP or IUI or embryo transfer date AND confirmatory ultrasound in first trimester
 
 OR 
 
○ First trimester ultrasound
 
 
 

2a	
 
• Weight below 10th percentile for gestational age AND
 
• The following used in assessment of weight: 
 
○ Newborn weighed within 24 hours of birth on any scale with a < 50 g resolution, tared to zero and calibrated
 
 AND
 
• The following for assessment of gestational age: 
 
○ Certain LMP with first or second trimester ultrasound
 
 OR 
 
○ Certain LMP with first trimester physical exam
 
 
 

2b	
 
• Weight below 10th percentile for gestational age AND
 
• The following used in assessment of weight: 
 
○ Newborn weighed within 24 hours of birth on any scale with a < 50 g resolution, tared to zero and calibrated
 
 AND
 
• The following assessment of gestational age: 
 
○ Uncertain LMP with second trimester ultrasound
 
 
 

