**Table 39 Preterm Birth**

Birth in less than 37 gestation-completed weeks (less than 259 days).

Prematurity and assessment of gestational age	
Level	Description
1	Certain last menstrual period date (LMP) LMP or intrauterine insemination (IUI) date or embryo transfer (ET) date with confirmatory 1st trimester scan ( $\leq 13 \frac{6}{7}$ weeks). OR 1st trimester scan ( $\leq 13 \frac{6}{7}$ weeks)
2a	Certain LMP* with 2nd trimester scan (14 $\frac{0}{7}$ weeks to 27 $\frac{6}{7}$ weeks). Note: If LMP and U/S do not correlate, default to U/S GA assessment. OR Certain LMP* with 1st trimester physical examination.
2b	Uncertain LMP with 2nd trimester scan (14 $\frac{0}{7}$ weeks to 27 $\frac{6}{7}$ weeks).
3a	Certain LMP with 3rd trimester scan $\geq 28 \frac{0}{7}$ weeks OR Certain LMP with confirmatory 2nd trimester Fundal Height (FH) OR Certain LMP with birth weight OR Uncertain LMP with 1st trimester physical examination.
3b	Uncertain LMP with FH. OR Uncertain LMP with newborn physical assessment. OR Uncertain LMP with Birth weight
*	Definitions of LMP, birth weight and physical assessment in referenced article.

Reference: Quinn JA, Munoz FM, Gonik B, et al. Preterm birth: Case definition & guidelines for data collection, analysis, and presentation of immunisation safety data. *Vaccine*. 2016;34(49):6047-6056.

**CONFIDENTIAL**207636 (EPI-RSV-008 BOD)  
Protocol Amendment 4 Final**Table 40 Failure to Thrive**

Failure to Thrive (FTT) can be broadly defined as a faltering of growth from a previously established pattern of growth. It is universally established that a diagnosis of failure to thrive should be based on anthropometric data. However no consensus exists as to which measurements achieve the highest specificity and sensitivity. Weight is generally regarded as the indicator of choice, particularly a change in growth velocity, and as such has been selected as the standard for this case definition with a weight for age deceleration as the primary indicator of failure to thrive. The case definition should be applied when there is no clear alternative diagnosis for the reported event to account for the combination of symptoms.

Level	Description
1	Infant age  determined by a documented birth date AND Weights obtained using an electronic scale AND At least 2 weights, measured at least 4 weeks apart AND Weight for age deceleration  through at least 2 centile spaces on growth chart 

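### Large for gestational age has two criteria that need not agree, and the protocol does not say which one governs at term

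*Protocol*

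**What the plan says.** Section 11.1.1.3 lists "Large for gestational age" as a primary neonatal event, with macrosomia as the next, separate item. Section 11.6 tabulates, for each event, "The number and percentage (with exact 95% CI) of neonates presenting the events of interest".

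Section 5.2 sends the reader to Appendix D for the detailed descriptions. Table 41 there gives:

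- LGA: "Birth weight > 90% for newborns of same gestational age in same population (>4000g at term").
- Macrosomia: "BW >4000 g (8 lb, 13 oz"), with no gestational-age condition.

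Two other tables help in reading these rows. Table 39 defines preterm birth as "Birth in less than 37 gestation-completed weeks (less than 259 days"), so term means 37 completed weeks or more. Table 31 defines small for gestational age (SGA), the mirror-image event, by a "percentile for gestational age as assessed against a validated global, regional or local standard". It has no gram cut-off.

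**The concern.** The first half of the LGA line is relative: it depends on gestational age and on population. The bracket is absolute: one weight for every term week and every country. A single gram value cannot be the 90th percentile at each week from 37 onwards, nor in every population. The protocol does not say whether the bracket replaces the percentile at term, adds to it or only illustrates it. It names no reference chart for LGA.

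The purpose of the study (Section 1.1) is to learn how often events occur in each setting where later vaccine trials may run, using standardised case definitions so that countries can be compared. If sites choose different halves of the line, a difference in definition looks like a difference between settings, and the overall analysis in Section 11.6 pools the two. If all sites follow the bracket, LGA adds nothing to macrosomia among term births.

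**Working it through.** **1. The plan's own precision figure.** Section 11.2 states: "Assuming a drop-out rate of about 10% during the course of follow-up", "there will be up to approximately 180 to 270 evaluable subjects by country". This reproduces: 200 × 0.9 = 180 and 300 × 0.9 = 270. Table 17 gives exact 95% limits. The Clopper-Pearson formula is: lower = Beta(0.025; x, n−x+1), upper = Beta(0.975; x+1, n−x). For a 10% event:

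| n | x | Recomputed | Table 17 |
|---|---|---|---|
| 270 | 27 | 6.7–14.2% | 6.7–14.2% |
| 180 | 18 | 6.0–15.3% | 6–15.3% |
| 100 | 10 | 4.9–17.6% | 4.9–17.6% |

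The other rows of Table 17 also reproduce to within 0.1 point.

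**2. The bracket applied at term.** Term LGA = {gestational age ≥ 37 weeks and weight > 4000 g}. Macrosomia restricted to term = {gestational age ≥ 37 weeks and weight > 4000 g}. These are the same set whatever the data, so count, percentage and interval coincide among term births. The two events can differ only in preterm births. No distributional assumption is needed.

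**3. The percentile applied.** If the reference matches the local population, about 10% exceed it: 18 of 180 or 27 of 270.

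**4. How far the two criteria can differ.** The protocol gives no mean or SD for birth weight, so these are assumptions. Take term weight as normal with mean μ and SD σ, one curve for all term weeks, and treat all evaluable infants as term births.

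- Share above 4000 g = 1 − Φ((4000 − μ)/σ)
- 90th percentile = μ + 1.2816σ

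With σ = 450 g:

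| μ (g) | (4000 − μ)/σ | Share > 4000 g | 90th percentile (g) | Expected > 4000 g in 180 | Expected > 4000 g in 270 |
|---|---|---|---|---|---|
| 3000 | 2.22 | 1.3% | 3577 | 2.4 | 3.5 |
| 3200 | 1.78 | 3.8% | 3777 | 6.8 | 10.2 |
| 3400 | 1.33 | 9.1% | 3977 | 16.4 | 24.6 |
| 3600 | 0.89 | 18.7% | 4177 | 33.7 | 50.5 |

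The percentile reading gives 18 and 27 in the last two columns. The criteria agree when μ = 4000 − 1.2816σ, which is 3487, 3423 and 3359 g for σ = 400, 450 and 500 g. Below that mean the fixed weight gives fewer cases than the percentile; above it, more. Over means of 2800 to 3600 g and SDs of 400 to 500 g, the share above 4000 g runs from 0.1% to 21%.

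**5. Against the plan's precision.** At n = 270 the sampling interval for a 10% event is 6.7–14.2%. The shares at 3000, 3200 and 3600 g fall outside it; the share at 3400 g falls inside. The same holds at n = 180.

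**The case against.** **The bracket may be only a gloss.** The sentence reads naturally with the percentile as the operative criterion and the gram figure as an illustration. A reader might infer from Table 41 that LGA and macrosomia are the same count at term. The documents do not support that outright: it follows only if the bracket governs at term, and nothing says that it does. What stands is that the line carries two criteria that can disagree and leaves the choice to whoever applies it.

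**Size and direction are assumed.** A reader who looks only at the lower means might infer that LGA would be too low by up to about eightfold (10 / 1.31 = 7.6 at 3000 g). The documents do not support this, because they give no birth-weight distribution and at an assumed mean of 3600 g the fixed weight overcounts. Only disagreement in either direction can be claimed.

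**Ten per cent is not a true rate.** A percentile taken from the study's own infants gives about 10% by construction; an external chart need not. This objection is sound. It means that removing the bracket without naming a reference would still let sites use different charts.

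**The consequence is limited.** The analysis is descriptive, Table 17 is generic over event rates of 0 to 35%, and no test or sample size depends on LGA. Overlap between events is not an error in itself; SGA and low birth weight also overlap. The inputs are recorded, so LGA could be derived centrally at analysis. All of this is fair and limits the weight of the point. A central derivation would still have to choose a criterion, and sites would still be recording events against an ambiguous definition.

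**Conclusion.** The point holds as a contradictory case definition for one primary neonatal event. That the two criteria cannot coincide for every term week and country, and that the bracket makes term LGA identical to term macrosomia if it is followed, needs no assumption. The size does: with SD 450 g and means of 3000 to 3600 g, the fixed weight would classify 1.3% to 18.7% of term infants as LGA, against about 10% by a matched percentile. Those means and the SD are assumptions, and neither the size nor the direction in any participating country can be read from the protocol. The effect is confined to the LGA estimate and its comparison across sites and countries. It should be corrected, but it does not affect the rest of the plan.

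**What to change.** In Table 41:

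- Delete the bracketed gram value from the LGA row.
- Define LGA only as birth weight above the 90th percentile for gestational age, against a stated reference standard of the same kind as Table 31 uses for SGA.
- Keep the 4000 g limit for macrosomia alone.

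Derive LGA centrally from recorded birth weight and gestational age, so that one rule applies everywhere. SGA and low birth weight already need birth weight, and Section 8.5.2 already records gestational age.

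The cost is a one-line change to a definition, the choice of a reference standard and one derived variable. No new data, visits or subjects are needed.

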## APPENDIX E AMENDMENTS AND ADMINISTRATIVE CHANGES TO THE PROTOCOL

GlaxoSmithKline Biologicals Vaccines R & D Protocol Amendment 1	
eTrack study number and Abbreviated Title	207636 (EPI-RSV-008 BOD)
Amendment number:	Amendment 1
Amendment date:	12-FEB-2018
Co-ordinating author:	PPD , Lead Science Writer
Rationale/background for changes: The protocol has been amended to reflect the following changes and provide the following clarifications / corrections. 
 
• A separate screening visit has been added.
 
• Evaluations of GBS rectovaginal colonization of pregnant women, and the occurrence of GBS bacteremia/septicemia in their newborn infants, have been removed as study objectives.
 
• The Study Procedures Table and Detailed Descriptions of Study procedures have been updated both for consistency with these changes, and for improved consistency with the content of the electronic Case Report Forms for the study.
 
• Parents / LARs/designates are to contact the study site whenever: 
 
– the infant has developed symptoms of respiratory tract infection (RTI),
 
– the infant has developed symptoms of difficulty in breathing or wheezing,
 
– the infant's RTI symptoms have worsened,
 
– the parent(s)/LAR(s) (or their designate(s)) are concerned about the infant's RTI signs and/or symptoms (parental concern).
 
 
 
• Text describing the content and use of the maternal health memory aid and the infant health and RTI memory aid has been updated and clarified.
 
• Additional editorial changes have been made to ensure consistency with the modifications noted above, and typographical errors have been corrected.
 
	

Text that has been moved or added is presented in ***bold italics*** and deleted text in ~~strike-through~~ in the following sections.

**Glossary**

Level 2 ultrasound ( or fetal morphology ultrasound )	Definition is unchanged. Only the label has been adjusted, as noted on the left.
Neonatal events of interest	Events as described in Section 11.1 that occur from birth through 28 days of age.
Pregnancy related events of interest	Events as described in Section 11.1 that occur from <del>post-enrolment</del> Visit 1 through Visit 6 (Day 42).
Protocol amendment:	The International Conference on Council for Harmonisation (ICH) .....
<del>Respiratory tract infection (RTI) with parental concern:</del>	<del>Any RTI for which the parents/ LAR(s) have visited or plan to visit a medical health care practitioner.</del>
End of Study (Synonym of End of Trial)	<del>For studies without collection of human biological samples or imaging data, EoS is the Last Subject Last Visit (LSLV).</del>

**Synopsis**

Number of subjects	Up Approximatey 4000 pregnant women (up to approximately 400 pregnant women <math>\geq 24^{0/7}</math> weeks and <math>< 28^{0/7}</math> weeks of gestation are planned to be enrolled per country.) Neonates of enrolled pregnant women who consent to the infant's continued study participation will also be enrolled.
Sampling schedule for neonates/infants	During the 1-year post-birth surveillance period, for each RTI with suspicion of difficulty in breathing, or wheezing, or with parental concern, a nasal swab will be collected <del>at the LRTI study visit a visit to assess potential LRTIs</del>

**Background and Rationale (Section 1.1 and Synopsis “Rationale for the Study and Study Design”)**

..... There are also a number of maternal vaccines in development that aim to protect neonates and infants from additional pathogens, including respiratory syncytial virus (RSV) and group B streptococcus (GBS). GlaxoSmithKline (GSK) will enter Phase II with its *is developing an* investigational vaccine for use in pregnant women, against RSV disease. GBS vaccines are also being developed by GSK. Of note, these vaccines are developed solely for immunization in pregnancy.

**CONFIDENTIAL**207636 (EPI-RSV-008 BOD)  
Protocol Amendment 4 Final

Maternal immunization is implemented worldwide and has the potential to make a major contribution to reducing RSV lower respiratory tract infections (LRTI) ~~GBS~~ and other disease burden in infants globally.

Whilst there is good documentation of the global burden of RSV disease, incidence of RSV-LRTI according to the World Health Organization (WHO) 2015 case definitions [Modjarrad, 2016] is lacking in the literature. Hence, this study will also estimate the incidence of infant RSV-LRTI using WHO case definitions across geographically distinct locations to support incidence rate assumptions for planning of future efficacy trials.

~~There are limited data on the prevalence of GBS rectovaginal colonization in pregnant women, by serotype, in different global settings and this study will aim to address this gap.~~

To achieve these goals, GSK will be guided by the WHO recommendations on antenatal care for a positive pregnancy experience [WHO, 2016] and the Global Alignment of Immunization safety Assessment in pregnancy (GAIA) case definitions [Bonhoeffer, 2016]. ~~Standardisation of surveillance methodology and case definitions (applicable to maternal immunization AEs) may support comparison of data across different countries [Jones, 2016 Bauwens 2016; Bonhoeffer 2016; Kochhar 2017].~~

### **Rationale for the Study Population (Section 1.1.1 and Synopsis)**

..... Regardless of enrolment location, healthy pregnant women aged 18 to 40 years with normal, uncomplicated, singleton pregnancies, who have had a ~~second trimester level 2 (fetal morphology)~~ ultrasound without any significant findings will be eligible for possible study participation. Inclusion / exclusion criteria have been structured in a way that resembles those of Phase ~~II/III exclusion~~ criteria to ensure good comparability

Pregnant women ~~will be enrolled starting at 240/7 and up to (but not including) 280/7 weeks of gestation will be enrolled~~, to ensure that they are followed as of the time of potential vaccination in a clinical trial.

### **Rationale for the Surveillance System for the detection of pregnancy related events of interest (Section 1.1.2)**

..... ~~Study Information obtained from~~ study-specific procedures and laboratory ~~testing tests~~ (e.g. blood sampling, vaginal swabs, urine dipstick) ~~will be performed for epidemiological purposes only; the information obtained from these procedures and tests is not to be relied upon for clinical management of study subjects.~~

### **~~Rationale for the inclusion of GBS serotyping and surveillance~~**

~~In addition to RSV, GSK is developing a GBS maternal vaccine. GBS is the leading cause of neonatal sepsis globally, and disease can occur from the time of birth through 3 months of age. There is a need to address some of the GBS knowledge gaps and if possible prepare sites to detect GBS invasive disease. Aligned with this strategy, this study may collect vaginal swabs and blood samples to assess GBS colonization and serotypes, and antibody levels in maternal and cord blood. Data regarding occurrence of GBS invasive disease (sepsis, pneumonia and meningitis) may be collected through 90 days after birth, if possible. In case of suspected neonatal sepsis, pneumonia or~~

**CONFIDENTIAL**207636 (EPI-RSV-008 BOD)  
Protocol Amendment 4 Final

~~meningitis, GBS culture results will be documented if performed by a local healthcare provider. Because GBS testing results from study vaginal swabs will be performed only for epidemiological purposes and will not be available in time to inform clinical management, the GBS portion of this protocol will only be implemented in settings that have ongoing routine implementation of risk-based intrapartum antibiotic prophylaxis for GBS. Vaginal swabs will only be performed in settings that adhere to this risk-based approach for intrapartum antibiotic prophylaxis.~~

